1.0 Background & Rationale

Vitamin D is derived from two sources: the skin (endogenous) and the diet (exogenous). It is generally believed that the major source of vitamin D is the exposure of the skin to UVB-rays contained in sunlight. However, the full characterization of the contribution of diet and sunlight to optimal vitamin D status remains unknown. Furthermore, the response of individuals to vitamin D supplementation is known to be variable in all population groups since several personal and environmental characteristics may affect the conversion of pre-vitamin D by sunlight, such as latitude, available UVB radiation throughout the year, skin pigmentation, age, individual behavior, diet and genetic factors. We urgently need to define more closely the interaction between nutrition and genetics in response to vitamin D supplementation. There is a considerable lack of data in both Brazil and UK populations. (Adams and Hewison, 2010; (Lanham-New et al, 2012)

Based on the important contribution of sunlight exposure to the production and maintenance of serum 25OHD levels, it would be reasonable to believe that vitamin D deficiency may be a problem restricted to countries situated at higher latitudes. However, several studies from sunny countries have shown that vitamin D deficiency is a more common phenomenon, despite the abundance of sunlight in these locations making it a global health problem. (Lips et al, 2001; Bandeira et al, 2010). Even though Brazil is geographically located such that there is potentially an abundance of sunlight and therefore of vitamin D available throughout the year, there is still evidence of sub-optimal levels of vitamin D in the population. A cross-sectional study conducted in Rio de Janeiro, (latitude 22 ° S), has shown a high incidence of inadequate serum 25 (OH) D (68.3 %) in healthy adults (Russo et al ,2009). Much of the UV in sunlight is absorbed by clouds, ozone and other forms of atmospheric pollution. In higher latitudes as the distance from the equator increases, zenith angle is increased during winter months and consequently, the UV radiation reaching the earth's surface is reduced, and therefore the cutaneous production of vitamin D3 is also reduced. (Lips et al 2006; Wacker and Holick, 2013). Thus, the cutaneous synthesis of vitamin D is expected to be greater in low-latitude regions due to greater exposure to UVB radiation. In the UK, there is no UV radiation of the appropriate wavelength (280mm-310mm) from the end of October to the end of March and for the remaining months of the year, 60% of the effective UV radiation occurs between 11.00am and 3.00pm. Moreover, studies have shown the influence of skin pigmentation in reducing the UVB-mediated synthesis of vitamin D. Greater quantification of the effect of sunlight exposure on vitamin D status is urgently required. Therefore, we wish to investigate the Brazilian population, suspecting that we could be underestimating the level of insufficiency or deficiency of vitamin D in this population, due to the false impression that the level of solar radiation would suffice for people living in sunny countries.

Recent studies have suggested that genetic variation could be a reasonable explanation to the considerable differences on vitamin D levels among population independently of latitude and sunlight exposure. (Valdivielso 2004) Heritability of vitamin D levels has been reported to range from 28.8% to 68.9% in an adolescent twin study and up to 80% in a genome-wide linkage scan. (Uinterlinden 2004, Santos 2012). Identifying genetic variants in the form of single nucleotide polymorphisms (SNPs) has been one of the key methods for identifying genetic variants associated with vitamin D levels. The data would be helpful for identifying those who may be at risk of deficiency and targeting treatment to reduce the impact of vitamin D deficiency. The study will undertake a Genome-wide analysis of leukocyte gene expression and its correlation with differences in vitamin D status. The Vitamin D Receptor (VDR) is a nuclear transcription factor which controls expression of a wide range of genes, including several that encode cytochrome P450 enzymes and cytokines. Human leukocytes are known to express the VDRencoding gene and it is therefore envisaged that differences in vitamin D responses of individuals could be reflected by differences in leukocyte gene expression. Therefore we propose to analyse genomewide transcriptomic expression within leukocytes of selected participants in order to associate specific signal transduction and metabolic pathways to respective vitamin D responses. Circulating 25(OH)D concentrations have been shown to be strongly related to SNPs located on exons of the vitamin D binding protein gene: i.e. minor SNP variants of DBP-1 (rs7041, GG®TT (17.5%) and DBP-2 (rs4588, CC®AA (9%), resulting in 10-13% lower circulating 25OHD levels.

Our results will firstly enable determination of how important (as a % contribution) diet, sunlight exposure and genetic factors are to vitamin D status when directly comparing, using the same methodology, same ethnicity populations living in a Southern Hemisphere (where there is abundant sunlight exposure) and in a Northern Hemisphere (where there is only sufficient sunlight exposure during the months April to September).

The data will provide both countries with key data on whether there should be consideration of further revisions to dietary recommendations for vitamin D in adult populations. This study provides good 'value for money' since it draws upon previously collected data in the UK and enables a strong study design to be conducted in the two Countries, simultaneously. The data will be of great interest to the field of Nutritional Sciences by the provision and formulation of data, within a short period of time, examining the interaction of diet and the environment on vitamin D status and its functional consequences. The '**systems level**' approach will enable us to identify differences in gene expression and whether this explains why some individuals are 'good' responders or 'poor' responders to vitamin D supplementation (Wang et al, 2010). This has never been done before in the field, by examining two population groups living in different countries but following identical study designs. Also, to our knowledge, this is the first randomized control trial to analyse the effect of vitamin D supplementation in Brazilian women, either living in the UK or in Brazil.

2.0 Objectives & Design

2.1 Primary Objectives: To examine the response (in vitamin D status) to vitamin D supplementation and sunlight exposure, and its influencing factors within and between Brazilian female adults living in the UK and Brazilian female adults living in Brazil.

2.2 Secondary Objectives

- (i) Analyze the difference regarding time and intensity of sun exposure between Brazilian women living in Brazil and Brazilian women living in the UK.
- (ii) Determine the prevalence of inadequate dietary Vitamin D intake in these women.
- (iii) Determine the prevalence of insufficient/deficient levels of vitamin D in these women.
- (iv) To elucidate the association between Vitamin D status and markers of calcium of calcium metabolism.
- (v) Examine the influence of latitude on vitamin D optimal levels.
- (vi) Analyze the influence of skin pigmentation on vitamin D optimal levels.
- (vii) Analyze if response to Vitamin D supplementation is dependent on initial vitamin D levels.
- (viii) Investigate the genetic and enzymatic mechanisms underlying the adolescents' response to vitamin D supplementation via genotyping for polymorphisms related to vitamin D metabolism and comparing the high and low responders to supplementation (Genetic Sub-Study).

2.3 Hypothesis

The study hypothesis that, during winter, vitamin D supplementation is required to obtain Vitamin D optimal levels in Brazilian women residing in the UK as well as Brazilian women residing in Brazil and that this response is dependent on the initial levels, being also influenced by sunlight exposure, skin pigmentation and polymorphisms of the vitamin D receptor gene.

H1: Dietary intakes of vitamin D are too low and sunlight exposure is insufficient for optimal vitamin D status in Brazilians living in the UK and Brazilians living in Brazil.

H2: The response of subjects to vitamin D supplementation is dependent on baseline 25OHD levels.

H3: Response to supplementation is influenced by sun light exposure.

H4: Skin pigmentation is an influential factor on vitamin D optimal levels.

H5: There will be strong genetic influences on 25OHD changes in response to vitamin D supplementation; these will be similar in both groups.

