3.0 Experimental Design

Two controlled, randomized, double-blind clinical trials will be developed and undertaken (one in Brazil and the other in the UK) with an intervention period of 12 weeks.

A questionnaire to screen for the relevant inclusion and exclusion criteria (see section A) will be administered in order to select 80 Brazilian female subjects, aged 20 to 59 years, in each of the two countries. The women selected will be randomly divided into two groups: Placebo Group and Supplemented Group, the latter will receive 600UI UI of vitamin D.

The first clinical trial will run in the UK from October 2016 to March 2017 (autumn-winter) and then the second will run in Brazil from April 2017 to September 2017 (autumn-winter). After the analysis of the effect of vitamin D supplementation compared to placebo, the results obtained in the supplemented group will also be analysed according to the genotypes for SNPs in the VDR gene.

We have chosen 12 weeks (3 months) as the supplementation period as we consider this to be ample time for 25OHD levels to rise (half-life of 25OHD is 3 weeks) and this has been demonstrated to be an effective timeframe for supplementation of vitamin D in previous studies.

We have chosen 600IU to enable the study to be relevant to the new IOM US recommendations for vitamin D, which are currently the reference document used in Brazil, even though the Brazilian nutritional table remains with the daily intake recommendation of 200 IU, which was the IOM recommendation in 1997. Compliance will be checked by compliance interviews during the trial and by empty packaging count.

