3.1 Sample Size and randomisation

A total of 80 subjects (at 90% power) are required for recruitment into the 600 IU vitamin D group vs placebo group for the RCT to be conducted in the UK and a total of 80 subjects (at 90% power) are required for recruitment into the 600 IU vitamin D group vs. placebo group for the RCT to be conducted in Brazil. This will enable us to detect a 0.6 SD size effect at 90% power in serum 25OHD levels between placebo and 600 IU in UK-dwelling Brazilian populations and Brazilians living in Brazil. These study numbers of 40 subjects for the vitamin D group and n 40 for the placebo group includes a 20% drop-out rate factored in.

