7.0 Study Evaluation and Statistical Analysis

Statistical analysis will be undertaken with support from the University of Surrey statistical department. Data will be checked for normality using appropriate testing. Appropriate parametric/non-parametric analysis will be applied.

The database will be stored and analysed using SPSS ® version 13.0.

The descriptive analysis, including mean ± standard deviation, median and lower limit and higher will be held for all quantitative variables Data will be checked for normality using appropriate testing. Appropriate parametric/non-parametric analysis will be applied. Student t test or Mann-Whitney test, depending on the distribution of data, will be applied to evaluate differences between supplemented and placebo. For analysis between Brazil and UK groups an ANOVA test will be undertaken. Linear correlation, Pearson or Spearman, will be calculated in accordance with the presence / absence of normal distribution, respectively, between vitamin D intake, sun exposure, skin pigmentation and vitamin D serum concentration. Multiple linear regression analysis will be performed to determine the variants that influence blood concentrations of vitamin D. In order to determine whether supplemental response differs between genotypes, these will be separated into wild homozygotes, heterozygotes and homozygotes for the variant. In this approach, the results will be evaluated with the test ANOVA or Kruskal-Wallis, in cases of variables with normal distribution or not, respectively. To describe the relationship between food intake aspects and features biochemical independent of energy intake, intake values of nutrients of interest will be adjusted to energy in accordance with the method. Significance considered as standard will be 5%.

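### H5 predicts similar genetic effects in both groups, but no planned analysis estimates how far those effects differ between the countries

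*Combined protocol and SAP*

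**What the plan says.** Section 2.3 states H5 as "There will be strong genetic influences on 25OHD changes in response to vitamin D supplementation; these will be similar in both groups". The first clause predicts an effect. The second predicts that the effect is alike in two groups.

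Section 3.0 says that, after the placebo comparison, "the results obtained in the supplemented group will also be analysed according to the genotypes for SNPs in the VDR gene". It also plans a genetic risk score from several vitamin D genes, but describes no comparison of that score's effect between countries.

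Section 7.0 gives the methods. For genotypes: "In order to determine whether supplemental response differs between genotypes, these will be separated into wild homozygotes, heterozygotes and homozygotes for the variant", and "the results will be evaluated with the test ANOVA or Kruskal-Wallis". For countries: "For analysis between Brazil and UK groups an ANOVA test will be undertaken". There is also a regression: "Multiple linear regression analysis will be performed to determine the variants that influence blood concentrations of vitamin D". The significance level is 5%, with sidedness not stated. None of these entries mentions a genotype-by-country term, a confidence interval for a country difference in genetic effect, or a definition of similar.

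The only power statement, in section 3.1, concerns the treatment comparison: "This will enable us to detect a 0.6 SD size effect at 90% power in serum 25OHD levels between placebo and 600 IU".

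**The concern.** A prediction of similarity needs an estimate of the difference and a measure of its precision. A test of whether genotypes differ within a country, or of whether the countries differ overall, supplies neither. If the genotype tests are run by country, as two separate trials invite, the results that lie side by side are two verdicts of significant or not significant.

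That comparison can fail both ways. Two non-significant results, or an undetected country difference, may reflect small numbers rather than similar effects. One significant and one non-significant result may reflect chance when the true effects are equal. At stake is what can be concluded on the second clause of H5. Section 2.1 makes influencing factors within and between the two populations part of the main objective, but the genetic work itself is secondary objective (viii), labelled a sub-study.

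**Working it through.** **The plan's own figure.** There is none for H5. The 0.6 SD at 90% power in section 3.1 is for placebo versus 600 IU. A plain two-sided calculation gives 2 × (1.960 + 1.282)² / 0.6² = 58.4, so 59 per arm before dropout, not 40. That is a separate matter; only the arm size is used here.

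**Inputs from the documents.** 40 supplemented women per country including 20% dropout (section 3.1), so 40 × 0.8 = 32 completers; 40 is also shown as the no-dropout case. Genotype analysis is in the supplemented group (section 3.0). Level 5% (section 7.0).

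**Assumptions.** Two-sided test. Allele frequency 0.30 with additive 0/1/2 coding, so genotype variance 2 × 0.30 × 0.70 = 0.42. This agrees with the 9% minor homozygotes that section 1.0 gives for rs4588 (0.30² = 0.09). Share of response variance explained by the SNP: 10%, 20% or 30%. The documents give no such share; the 10-13% in section 1.0 concerns 25OHD level, not response. Effects are in residual SDs of the 25OHD change.

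**Step 1: precision of the country difference.**
- 32 per country: SE of one per-allele effect = √(1/(32 × 0.42)) = 0.273. SE of the difference = √2 × 0.273 = 0.386. With 64 − 4 = 60 df, t = 2.000, so the 95% half-width is 0.77 SD.
- 40 per country: SE 0.244, difference 0.345, 76 df, t = 1.992, half-width 0.69 SD.

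**Step 2: effect in one country, none in the other.** Per-allele effect β = √(R²/(1 − R²)/0.42). Power of an interaction test comes from the noncentral t with noncentrality β / SE of the difference.

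| R² in one country | β (SD) | Noncentrality, n = 32 | Detected, n = 32 | Detected, n = 40 |
|---|---|---|---|---|
| 10% | 0.51 | 1.33 | 26% | 31% |
| 20% | 0.77 | 2.00 | 50% | 60% |
| 30% | 1.01 | 2.62 | 73% | 82% |

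**Step 3: separate tests in each country, n = 32.** At R² = 10%, each country's own test has noncentrality 0.514/0.273 = 1.89 on 30 df and power 0.446.
- Same effect in both countries: the tests disagree with probability 2 × 0.446 × 0.554 = 0.49. For the same 20% or 30% effect, with power 0.781 and 0.948, this falls to 0.34 and 0.10.
- Effect in one country only: they disagree with probability 0.446 × 0.95 + 0.554 × 0.05 = 0.45, so they agree in 55% of trials.

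At 10% explained, disagreement is about as likely when the effects are equal as when one is absent. It carries almost no information.

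**Step 4: cross-check with two genotype classes.** With a 50/50 split and 32 per country, the SE of the country difference is √(2 × (1/16 + 1/16)) = 0.50. A one-country effect of 0.6 SD is detected in 22% of trials (27% with 40). With a 9% genotype share it is 11%. The conclusion does not depend on the additive model.

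**The case against.** The strongest objection is that H5 predicts strong effects, and low detection belongs to weaker ones. This stands. At 20% of variance explained, detection is an even chance with 32 per country, and at 30% it is 73%. A risk score may explain more than a single SNP. A reader might infer that an effect confined to one country would usually go unnoticed. That is supported only for effects explaining clearly less than 20% of response.

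Second, the detection rates describe an interaction test that the plan does not name. A reader might take the complement of 26% as the share of trials in which this plan would declare similarity. The documents do not support that: they give no decision rule and never say that a non-significant result will be read as similarity, or discordant p-values as a difference. The rates show what data of this size could reveal, not what the investigators will conclude.

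Third, the planned regression and genotype means could be compared by size across countries, and section 7.0 does not exclude a country term. True, but it does not specify one, and that is the gap.

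Fourth, section 3.0 uses the word groups for placebo and supplemented. The country reading is still more natural: section 7.0 speaks of Brazil and UK groups, and response by genotype is studied only in supplemented women.

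Finally, this is one clause of the last of five hypotheses. That limits its weight but does not remove it.

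**Conclusion.** The point holds in a limited form. H5 predicts similarity and no stated analysis can address it. With 32 to 40 supplemented women per country, the country difference in per-allele effect would be known only to within about ±0.69 to ±0.77 SD. This is wider than the whole effect of a SNP explaining 10% of response (0.51 SD). Judging by separate significance tests would be unreliable in both directions at that effect size, and less so for larger effects.

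The figures rest on the assumed allele frequency, the assumed variance explained, two-sided 5% tests and genotyping of all supplemented completers. Section 3.0 reads that way. The DNA profiling paragraph in section 4.1 could be read as limiting genotyping to 48 selected samples, which would change the figures.

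A reader might infer that a formal equivalence test is needed. The documents give no margin, and one tied to the observed effect, such as half of it, would not be fixed in advance. In these scenarios it would be 0.51/2 = 0.26 SD or 0.77/2 = 0.39 SD, which a half-width of 0.77 SD cannot meet. Estimation is the realistic aim. The placebo versus 600 IU comparison is not affected.

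**What to change.** Add one prespecified analysis to section 7.0. In the supplemented women of both trials, model the 25OHD change on the genetic risk score (or the per-allele effect for a named SNP), country and their interaction. Report each country's effect and the country difference with its 95% CI. State that a non-significant country difference will not be read as similarity, and that significance in one country only will not be read as a difference. Reword the second clause of H5 as an aim to estimate the country difference in genetic effect, and say that the groups meant are the two countries.

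The cost is wording and one model; no extra participants or measurements are needed. The downside is that the interval will be wide and similarity will almost certainly not be established.

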3.0 Experimental Design

Two controlled, randomized, double-blind clinical trials will be developed and undertaken (one in Brazil and the other in the UK) with an intervention period of 12 weeks.

A questionnaire to screen for the relevant inclusion and exclusion criteria (see section A) will be administered in order to select 80 Brazilian female subjects, aged 20 to 59 years, in each of the two countries. The women selected will be randomly divided into two groups: Placebo Group and Supplemented Group, the latter will receive 600UI UI of vitamin D.

The first clinical trial will run in the UK from October 2016 to March 2017 (autumn-winter) and then the second will run in Brazil from April 2017 to September 2017 (autumn-winter). After the analysis of the effect of vitamin D supplementation compared to placebo, the results obtained in the supplemented group will also be analysed according to the genotypes for SNPs in the VDR gene.

We have chosen 12 weeks (3 months) as the supplementation period as we consider this to be ample time for 25OHD levels to rise (half-life of 25OHD is 3 weeks) and this has been demonstrated to be an effective timeframe for supplementation of vitamin D in previous studies.

We have chosen 600IU to enable the study to be relevant to the new IOM US recommendations for vitamin D, which are currently the reference document used in Brazil, even though the Brazilian nutritional table remains with the daily intake recommendation of 200 IU, which was the IOM recommendation in 1997. Compliance will be checked by compliance interviews during the trial and by empty packaging count.

We will genotype vitamin D related genes in DNA isolated from the study blood samples, DNA will be extracted and vitamin D polymorphisms will be determined by our genetic labs. These will include known candidate variants (VDR, vitamin D binding protein, CYP2R1, CYP27A1, CYP27B1, and CYP24A1), as well as variants identified by the ongoing genome-wide association analyses on 25OHD. We will construct a genetic risk score based on these polymorphisms. The Genome-wide expression profiling of RNA from leukocytes will focus on 48 participants (each at two sampling time points) that represent equally both groups, encompassing the best and worst supplementation-responders in each group. We will identify the complete spectrum of genes that are, by statistical criteria, either significantly up-or down-regulated (i.e. differentially expressed) between groups. The major comparison will be between the 'good' and 'poor' responders in each group; gene expression prior to supplementation will be compared to after supplementation for each subject analysed.

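### The between-country objective and H2 ask what modifies the supplement effect, but section 7.0 names no arm-by-factor term, no test for H2 and no definition of response

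*Combined protocol and SAP*

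**What the plan says.** **Questions.** The primary objective (section 2.1) concerns response to supplementation and what influences it "within and between Brazilian female adults living in the UK and Brazilian female adults living in Brazil". Secondary objective (vii) is to "Analyze if response to Vitamin D supplementation is dependent on initial vitamin D levels". Section 2.3 states H2 as "The response of subjects to vitamin D supplementation is dependent on baseline 25OHD levels", H3 as "Response to supplementation is influenced by sun light exposure" and H5 as "There will be strong genetic influences on 25OHD changes in response to vitamin D supplementation; these will be similar in both groups".

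**Analyses.** Section 7.0 names:
- a t test or Mann-Whitney test between supplemented and placebo, without saying whether the variable is final level or change;
- for country, "For analysis between Brazil and UK groups an ANOVA test will be undertaken", with no outcome or factors given;
- correlations of vitamin D intake, sun exposure and skin pigmentation with serum concentration;
- a multiple regression on blood concentration, with no terms listed;
- for genotype, "In order to determine whether supplemental response differs between genotypes, these will be separated into wild homozygotes, heterozygotes and homozygotes for the variant", followed by ANOVA or Kruskal-Wallis with no mention of arm.

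Section 3.0 adds that "the results obtained in the supplemented group will also be analysed according to the genotypes for SNPs in the VDR gene". It also speaks of good and poor responders without a metric or cut-off.

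**Size.** Section 3.1 plans 40 women per arm in each country, with 20% drop-out included, for a 0.6 SD difference between arms.

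**The concern.** Whether a factor modifies the effect of a supplement is a question about the difference between arms: does that difference vary with the factor? A factor-by-arm term answers it. No such term is named for any factor, and H2 has no named test at all.

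Three things are at stake.

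1. **Country.** A supplement effect that is significant in one trial and not in the other does not show that the two effects differ.
2. **Baseline.** Within a single arm, baseline is related to outcome without any effect modification. Women with low baselines tend to rise and women with high baselines tend to fall (regression to the mean), so change is negatively related to baseline. Final level is positively related to baseline, because women keep their rank. The two choices of outcome give spurious associations of opposite sign, and the plan does not choose between them.
3. **Genotype (secondary).** In supplemented women alone, a genotype difference in modification of the supplement effect looks the same as a genotype difference that would have appeared on placebo.

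**Working it through.** **The plan's own figure.** There is none for effect modification. Section 3.1 gives only the arm comparison: 0.6 SD, 90% power, 40 per arm including 20% drop-out, so 40 × 0.8 = 32 evaluable. At 32 per arm the two-sample normal formula (two-sided 5%; sidedness is not stated) gives SE = √(2/32) = 0.25 SD and power Φ(0.6/0.25 − 1.96) = Φ(0.44) = 67%, so 90% is not reproduced. That is a separate matter. Only the 32 is used here.

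**Country, judged by two separate tests.** Suppose the true effect is 0.6 SD in both countries and each trial has 67% power. The chance that exactly one trial is significant is 2 × 0.67 × 0.33 = 44%, although the effects are equal.

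**Baseline, tested in one arm only.** Assume equal SDs at baseline and final visit, correlation r between them, and the same supplement effect at every baseline. Then corr(baseline, change) = −√((1 − r)/2). The documents give no r, so a range is shown. The entries are the share of simulated trials (20,000 each) significant at 5%:

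| r | corr(baseline, change) | change, n = 32 | change, n = 64 | final level, n = 32 |
|---|---|---|---|---|
| 0.5 | −0.50 | 85% | 99% | 85% |
| 0.7 | −0.39 | 61% | 89% | >99% |
| 0.9 | −0.22 | 23–24% | 43% | 100% |

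n = 64 is the supplemented women of both countries together. Under the same assumptions the arm × baseline term, fitted on both arms, rejects in about 5%.

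**Why both interactions belong in one model.** Take 32 per cell, r = 0.7, no baseline modification within either country, and an assumed 1 SD gap in mean baseline between countries. In a pooled ANCOVA with arm × baseline but without arm × country, the arm × baseline test rejects in 8% of trials if the supplement effect differs between countries by 0.3 SD, and in about 18% if it differs by 0.6 SD. With both terms it rejects in about 5%.

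**Power for arm × country, 0.6 SD.** SE = √((4/32)(1 − r²)).
- Unadjusted (r = 0): SE 0.354, power Φ(0.6/0.354 − 1.96) = 40%.
- r = 0.7: SE 0.252, power 66%.
- r = 0.7 with arm × baseline also in the model and the 1 SD gap: country explains 0.25/1.25 = 0.20 of baseline variance, so the SE is multiplied by √(1/0.8) = 1.118, giving 0.282 and power 57%.

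**Genotype in supplemented women only**, with no true effect on response (r = 0.7, assumed allele frequency 0.30 or 0.42). ANOVA of change rejects in 4.6–5.6%. If untreated change also differs by an assumed 0.2 SD, this becomes 6.4–7.3% at n = 32 and 8.2–9.2% at n = 64. A stable genotype effect on level cancels out of change but not out of final level.

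**The case against.** The best defence is that the plan is underspecified rather than wrong. Section 7.0 uses a t test for the two arms and switches to ANOVA for the countries, which is compatible with a four-cell analysis including arm. The regression could likewise hold baseline, arm and their product. This stands in part: neither is excluded. But neither is stated, and the primary objective depends on it.

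A reader might infer from section 3.0 that H2 will also be tested in supplemented women only, and so that the plan carries an 85% false-positive rate. The documents do not support this. The supplemented-only statement covers VDR genotypes, and no section says how H2 will be tested. The percentages describe one analysis the plan leaves open, at assumed correlations.

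A reader might also extend the restriction to all the genetic work. Section 3.0 describes wider genotyping, a risk score and expression profiling in both groups without limiting them to the supplemented arm, so the restriction should be read as applying to the VDR analysis alone.

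On genotype, the defence is strong. H5 speaks of changes in 25OHD. If change is the outcome, the one-arm ANOVA holds about its nominal 5% unless untreated change differs by genotype, and a genotype × arm test has less power. That is why genotype is a secondary remark here.

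**Conclusion.** The concern holds as a gap in specification. The between-country part of the primary objective, and H2 with objective (vii), need arm-by-factor tests. None is named, H2 has no test, baseline 25OHD is in no named analysis, and response has no formula (H5 leans to change). These statements rest on the text alone.

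The size of the H2 hazard is illustrative: from 23–24% to 85% false positives for change at n = 32 as the assumed correlation falls from 0.9 to 0.5, against about 5% for arm × baseline. The genotype risk is small if change is analysed.

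It would be wrong to conclude that the trial's main result is compromised. The supplemented-versus-placebo comparison within each country is randomised and is not invalidated by any of this.

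**What to change.** In section 7.0:

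1. Define response once, as the supplemented-minus-placebo difference in week-12 25OHD adjusted for baseline 25OHD.
2. Use baseline-adjusted ANCOVA within each trial for the arm effect.
3. For the between-country question and H2, fit one ANCOVA on both arms of both trials with baseline, arm, country, arm × country and arm × baseline together. Arm × country then compares the countries' supplement effects at the same baseline, and arm × baseline tests H2 and objective (vii).
4. Report each interaction with its 95% CI, and do not read a non-significant one as evidence that the effects are similar.
5. State that arm × country compares randomised effects between non-randomised populations studied in different calendar periods.
6. Report genotype × arm, using all consenting women with DNA in both arms, as a supporting analysis beside the planned supplemented-group analysis.

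**Cost.** This is mainly wording, with no added recruitment or visits. Blood for genetic profiling is already planned for every woman, but any placebo samples not already planned for genotyping would have to be run, subject to consent. The real downside is power. Arm × country has the 40% to 66% shown above. For an assumed 0.6 SD difference in response between homozygotes, genotype × arm has 24–29% at 64 per arm, against 39–45% for the supplemented-only ANOVA of change.

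Sections 3.0 and 4.1 also differ on who is genotyped (the study samples, or 48 selected women). That is a separate point to reconcile.
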